#### Intraocular pressure

Number and percentage of patients with clinically intraocular pressure above 30 mmHg will be summarized by time windows. For patients with such values, a listing will also be provided.

#### Optical Coherence Tomography (OCT) and Fluorescein Angiography (FA)

The clinical outcome presented in the listing combine the clinical observation (present, not clinically significant and clinically significant) and the eye involvement (unilateral or bilateral). For each considered category, the number of subjects with at least one newly occurring abnormalities (whatever the clinical significance and clinically significant abnormalities) will be described by type of abnormality, on the subjects at risk of developing the abnormality (*i.e.* with baseline not missing and not being significantly abnormal in both eyes, and with at least one post-baseline value). Patients without baseline assessment will also be considered at risk at baseline of developing a new abnormality. For each considered category in each assessment (OCT and FA), newly occurring abnormalities will be provided.

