8.3.6. Ophthalmic Assessments

During the Main study period, visual assessment must be performed by investigator, to assess general inspection of the eyes, examination of motility and alignment, visual disturbance including diminished central vision, blurred vision or loss of vision at each Day 1, if clinically indicated at D8, D15, D22 during treatment and at 30-days follow-up visit.

During the Study extension period, visual assessment must be performed by investigator, to assess general inspection of the eyes, examination of motility and alignment, visual disturbance including diminished central vision, blurred vision or loss of vision at each Day 1, if clinically indicated at D15 during treatment and at 30-days follow-up visit.

At screening, EOT, if clinically indicated, during treatment, and at safety 30 day-follow-up visit in case of ocular clinical event at EOT visit, a full ophthalmic examination will be performed by an ophthalmologist (during Main study and Study extension periods).

The full ophthalmic examination includes:

- Best corrected visual acuity for distance testing, slit lamp examination, intraocular pressure and dilated fundoscopy (with attention to retinal abnormalities, especially retinal pigment epithelial detachment (RPED), serous detachment of the retina and RVO).
- OCT will be performed systematically at screening and if clinically indicated during treatment and at EOT.
- Fluorescein angiography will be performed only if clinically indicated from screening to EOT.

For all subjects, ophthalmic assessments may be performed more frequently per standard of care or if clinically indicated for evaluation of any visual signs or symptoms. Subjects with clinical suspicion of retinal abnormalities (i.e., RPED, posterior uveitis, serous detachment of the retina, RVO, photopsia, metamorphopsia, impairment of visual acuity, etc.), must complete at least one of the following additional assessments:

- For non-vascular abnormalities: OCT of the macula (spectral domain OCT recommended).
- For vascular abnormalities: fluorescein angiography of the central 30 degrees.

Images/results of the ophthalmic examinations (at a minimum, OCT and/or fluorescein angiography) should be sent to the study site and be maintained in the subject's source document file. These images/results may be requested to be sent to the Sponsor or designee.

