#### Fundoscopy and slit lamp

For each considered category (fundoscopy and slit lamp), the number of subjects with at least one newly occurring abnormalities (whatever the clinical significance) will be described by type of abnormality, on the subjects at risk of developing the abnormality. Subjects at risk of developing

the abnormality will be defined as subjects with baseline not missing and not being abnormal (whatever the clinical significance) in both eyes, and with at least one post-baseline value).

Same analysis will be performed for the number of subjects with at least one newly occurring clinically significant abnormalities. Subjects at risk of developing the abnormality will be defined as subjects with baseline not missing and not being clinically significantly abnormal in both eyes, and with at least one post-baseline value).

Subjects with newly occurring abnormalities in fundoscopy and slit lamp respectively will be tabulated in a listing of individual data.

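### The OCT and fluorescein-angiography at-risk set uses one baseline exclusion for two different counts and admits subjects without a baseline, unlike the rules for the visual assessment, fundoscopy and slit lamp

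*SAP*

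**What the plan says.** The OCT and FA paragraph of SAP Section 15.10 describes subjects with at least one newly occurring abnormality in two versions: "whatever the clinical significance and clinically significant abnormalities) will be described by type of abnormality". Both versions use one at-risk set, namely subjects "with baseline not missing and not being significantly abnormal in both eyes, and with at least one post-baseline value". The sentence that follows widens it: "Patients without baseline assessment will also be considered at risk at baseline of developing a new abnormality". That sentence carries the marker for footnote 3. The text of the footnote is missing from the copy of the SAP available for this review, and it may explain the rule.

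The next paragraph, on fundoscopy and slit lamp, keeps the two counts apart. For any abnormality, its rule reads: "the abnormality will be defined as subjects with baseline not missing and not being abnormal (whatever the clinical significance) in both eyes". For the clinically significant count, its rule reads: "Subjects at risk of developing the abnormality will be defined as subjects with baseline not missing and not being clinically significantly abnormal in both eyes". Both sets also need a post-baseline value. The visual-assessment paragraph of the same section has the same two-set structure.

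On availability of a baseline, Protocol Section 8.3.6 says "OCT will be performed systematically at screening and if clinically indicated during treatment and at EOT" and "Fluorescein angiography will be performed only if clinically indicated from screening to EOT".

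The SAP version log (Section 3) shows what was intended. A Version 2 entry says that the OCT and FA at-risk definition was changed to agree with fundoscopy and slit lamp, on the ground that both examinations were non-optional. A Version 4 entry for Section 15.10 says that the at-risk definition was clarified to separate all abnormalities from clinically significant ones.

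**The concern.** Two features of the OCT and FA paragraph affect what its proportions mean.

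First, the exclusion is set at the clinically significant level, but it also serves the any-significance count. A subject who already has non-significant abnormalities in both eyes has limited scope to show a new abnormality of any kind. The companion paragraphs drop such a subject from that count, and this one keeps the subject in. The Version 4 split reached the visual-assessment and fundoscopy/slit-lamp paragraphs but not this one.

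Second, a finding in a subject with no baseline cannot be classed as new or pre-existing, yet the added sentence places that subject among those at risk of a new one. FA is the examination for which a baseline may be lacking by design, because Protocol Section 8.3.6 makes it conditional from screening onwards. The non-optional premise in the Version 2 log entry does not fit FA as the protocol now describes it.

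At stake is whether the OCT and FA figures can be read next to the fundoscopy and slit-lamp figures, and whether *newly occurring* means the same thing in each. Retinal events are an anticipated toxicity of this regimen, so these tables will be read.

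**Working it through.** The plan states no count, rate or denominator for these outputs, so there is no figure to reproduce. The rules are compared first, and then their effect is shown with assumed inputs. The at-risk set is taken as the denominator, since Section 15.10 describes the counts on it, although the general convention in SAP Section 9.2 is the analysis population.

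**1. The rules side by side**

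| Examination | Removed from the any-abnormality count | Removed from the clinically significant count | Baseline needed |
|---|---|---|---|
| Visual assessment | any abnormality, both eyes | clinically significant, both eyes | yes |
| Fundoscopy, slit lamp | any abnormality, both eyes | clinically significant, both eyes | yes |
| OCT, FA | significant, both eyes | significant, both eyes | yes, then waived |

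If *significantly* means *clinically significantly*, the exclusion in the OCT and FA row is right for the clinically significant count. Only the any-abnormality count is affected.

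**2. Effect of the shared exclusion**

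Let N be subjects with a baseline, a post-baseline value and no significant bilateral baseline finding. Let b be those among them with non-significant findings in both eyes, e the new findings in the other N − b, and f the new findings in the b.

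- Fundoscopy rule: e/(N − b)
- OCT and FA rule: (e + f)/N

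Assume N = 90, b = 10, e = 20:

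- Fundoscopy rule: 20/80 = 25.0%
- OCT and FA rule, f = 0: 20/90 = 22.2%
- OCT and FA rule, f = 5: 25/90 = 27.8%

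The rules agree when f/b = e/(N − b), here f = 2.5, since 22.5/90 = 25.0%. Below that the OCT and FA rule understates, and above it the rule overstates.

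A second set of assumptions has 90 subjects, 2 with clinically significant findings in both eyes, a 20% rate of new findings in subjects with clean baselines, and f = 0:

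- b = 0: 17.6/88 = 20.0% under both rules
- b = 10: 15.6/78 = 20.0% against 15.6/88 = 17.7%
- b = 20: 13.6/68 = 20.0% against 13.6/88 = 15.5%

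**3. Effect of adding subjects without a baseline**

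If m subjects lack a baseline, p is the prevalence of pre-existing findings and r the rate of new ones, the expected number reported as new among them is m × [p + (1 − p) × r]. Taken alone, this pushes the proportion up.

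*OCT.* Take m = 10 of the 90, b = 0, p = 2/90 and r = 0.20. The added count is 10 × (0.022 + 0.978 × 0.20) = 2.2. The result is (15.6 + 2.2)/88 = 20.2%, against 15.6/78 = 20.0%.

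*FA.* Assume 10 subjects with a post-baseline FA, p = 0.10 and r = 0.30, so each subject without a baseline contributes 0.10 + 0.90 × 0.30 = 0.37.

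- 5 lack a baseline: 1.5/5 = 30.0% against (1.5 + 1.85)/10 = 33.5%
- 8 lack a baseline: 0.6/2 = 30.0% against (0.6 + 2.96)/10 = 35.6%
- all 10 lack a baseline: nobody at risk against 3.7/10 = 37.0%

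**4. Both together (OCT)**

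With m = 10, b = 10, 2 clinically significant in both eyes, p = 12/90, r = 0.20 and f = 0, the added count is 10 × (0.133 + 0.867 × 0.20) = 3.07. The result is (13.6 + 3.07)/88 = 18.9%, against 13.6/68 = 20.0%. Here the two effects partly cancel.

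**The case against.** The strongest reply is that the paragraph can be programmed as written. The word *also* can be read as adding a second group to the first, which gives a computable union, so a reader who inferred that the denominator is undefined would be going too far. A no-baseline rule has an obvious purpose for an examination done only when indicated, and counting unknown-baseline findings as new errs towards overstating risk. Footnote 3 may say exactly this, and its absence from the available copy is not a fault of the plan. All of that stands. What remains is that the union departs from the companion rules and from the alignment recorded in the version log.

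A reader might also infer that persisting baseline findings would be counted as new, which with the first inputs above gives 30/90 (33%). The documents do not support that. Where a baseline exists, a documented persisting finding is not *newly occurring* in the plan's own terms.

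Keeping a subject with one non-significant finding at risk of a different type of finding is not unreasonable in itself, since the counts are by type. But the same could be said of fundoscopy and slit lamp, where the plan chose otherwise.

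Finally, these tables are not the only view of retinal safety. SAP Section 15.2 summarises adverse events of special interest by grouping, Section 15.10 names two retinal groupings among them, and all eye examinations are listed individually. Dose rules act on the individual subject's grade, not on these tables. That limits the consequence but does not remove the inconsistency.

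**Conclusion.** The point holds as an inconsistency in a descriptive safety output. The shared exclusion leaves bilateral non-significant baseline findings in the any-abnormality denominator for OCT and FA. The no-baseline sentence lets findings of unknown onset be reported as new, chiefly for FA. For OCT the second feature should matter little, because the scan is planned for everyone at screening.

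It would be tempting to say that the reported rate of new retinal abnormalities is wrong. The documents do not support that: no rate or count is given, and with no missing baselines and no bilateral non-significant findings every reading gives the same answer. The size is unknown and the direction can go either way. On the assumed inputs, the shared exclusion moves OCT from 25% to 22% when none of the retained subjects has a new finding. For FA, the baseline rule decides most or all of the denominator if few subjects had a baseline FA, and that is an inference from the schedule, not a stated number.

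SAP Section 8 treats everything other than the primary test as exploratory, and the primary analysis is not touched. This is a minor point, worth correcting because it is cheap.

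**What to change.** In SAP Section 15.10, replace the single OCT and FA at-risk definition with the two sets already written for fundoscopy and slit lamp. For any abnormality, require a baseline that is not abnormal in both eyes, whatever the significance. For clinically significant abnormalities, require a baseline that is not clinically significantly abnormal in both eyes. Both need at least one post-baseline value.

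Delete the sentence that adds subjects without a baseline, or reconcile it with footnote 3. Report those subjects, chiefly for FA, on a separate line labelled *post-baseline abnormality, baseline unknown*, with their own denominator.

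The cost is a few sentences and a small programming change, with no new data. The drawback is that the FA at-risk set may be very small or empty, but the separate line keeps the information without calling it newly occurring.

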#### Fundoscopy and slit lamp

For each considered category (fundoscopy and slit lamp), the number of subjects with at least one newly occurring abnormalities (whatever the clinical significance) will be described by type of abnormality, on the subjects at risk of developing the abnormality. Subjects at risk of developing

the abnormality will be defined as subjects with baseline not missing and not being abnormal (whatever the clinical significance) in both eyes, and with at least one post-baseline value).

Same analysis will be performed for the number of subjects with at least one newly occurring clinically significant abnormalities. Subjects at risk of developing the abnormality will be defined as subjects with baseline not missing and not being clinically significantly abnormal in both eyes, and with at least one post-baseline value).

Subjects with newly occurring abnormalities in fundoscopy and slit lamp respectively will be tabulated in a listing of individual data.

### **15.11. CONCOMITANT THERAPIES AND THERAPEUTIC / DIAGNOSTIC PROCEDURES**

Concomitant therapies (as described in PRIOR AND CONCOMITANT THERAPY eCRF page) prior to and after the start of the study treatment will be tabulated from a descriptive perspective by therapeutic area according to the WHO-DRUG dictionary using the "anatomical therapeutic chemical (ATC) classification (ATC2, ATC4 and Preferred Term) for the FAS and according to the first study treatment administration:

- starting between informed consent signature and start of study treatment, and ending prior to the start of study treatment,
- starting prior to the start of study treatment and continuing after the start of study treatment,
- starting on or after the start of study treatment but no later than 30 days (included) after last dose of study drug.

The number and percentage of subjects with at least one concomitant therapeutic / diagnostic procedure (as described in MEDICAL AND SURGICAL PROCEDURES eCRF pages) will be tabulated by SOC and PT using the MedDRA terminology and according to the first study treatment administration.

The number and percentage of subjects with at least one antineoplastic therapy since study treatment discontinuation (as described in ANTI-NEOPLASTIC THERAPY SINCE STUDY TREATMENT

DISCONTINUATION - MEDICATION eCRF page) will be described by treatment intent (palliative, curative, unknown).

The number and percentage of subjects with at least one single agent since study treatment discontinuation (as described in ANTI-NEOPLASTIC THERAPY SINCE STUDY TREATMENT DISCONTINUATION - MEDICATION eCRF page) will be provided by WHO-DRUG ATC2, ATC4 and Preferred Term.

The number of patients with at least one combination identified in Appendix 1 with start dates within the same month or treatments taken in parallel despite being started within the same one month interval will be tabulated. The number and percentage of subjects with at least one antineoplastic surgery since study treatment discontinuation (as described in ANTI-NEOPLASTIC THERAPY SINCE STUDY TREATMENT DISCONTINUATION - SURGERY eCRF page) will be described by treatment intent, location of surgery and result. Location will be classified as done for primary tumor location (cf. Table 9).

The number and percentage of subjects with at least one antineoplastic surgery since study treatment discontinuation (as described in ANTI-NEOPLASTIC THERAPY SINCE STUDY TREATMENT DISCONTINUATION – SURGERY eCRF page) will be tabulated by SOC and PT using the MedDRA terminology.

The number and percentage of subjects with at least one antineoplastic radiotherapy since study treatment discontinuation (as described in ANTI-NEOPLASTIC THERAPY SINCE STUDY TREATMENT DISCONTINUATION – RADIO THERAPY eCRF page) will be tabulated by treatment intent (palliative, curative, unknown), best overall response and procedure linked to Chemotherapy (No/Yes).

Time to subsequent therapy (TST) will be defined as the time from the first study treatment administration to the initiation of subsequent antineoplastic therapy or death. TST will be described using survival curves according to the Kaplan Meier method and reporting estimated median (in months) with 95% CI, 25th and 75th percentiles and KM estimated probabilities with corresponding 95% CIs at several time points (every 2 months up to 14 months).

**Table 17: Censoring rules for TST**

In the below table, “subsequent antineoplastic therapy” refers to any additional secondary antineoplastic medication or anti-cancer surgery or radiotherapy.

	Situation	Event Date	Outcome
A	Initiation of subsequent antineoplastic therapy	Start date of subsequent antineoplastic therapy	Event
B	Death at any time after the first study treatment administration	Date of death	Event
C	Patient alive without starting a subsequent antineoplastic therapy	Date of last contact	Censored

PFS after next line of treatment (PFS2) will be defined as the time from the first study treatment administration to the earlier of death at any time after the first study treatment administration or progression after the start of subsequent anticancer therapy.

PFS2 will be described using survival curves according to the Kaplan Meier method and reporting estimated median (in months) with 95% CI, 25th and 75th percentiles and KM estimated probabilities with corresponding 95% CIs at several time points (every 2 months up to 14 months).

**Table 18: Censoring rules for PFS2**

In the below table, “subsequent antineoplastic therapy” refers to any additional secondary antineoplastic medication or anti-cancer surgery or radiotherapy.

	Situation	Event Date	Outcome
A	Progression after start of subsequent antineoplastic therapy	Date of progression	Event
B1	Death at any time after the first study treatment administration and before the start of any subsequent antineoplastic therapy, after zero or one missed/inadequate tumor assessment while on the Study	Date of death	Event
B2	Death at any time after the first study treatment administration and before the start of any subsequent antineoplastic therapy, after 2 or more missed/inadequate tumor assessments while on the Study	Date of last contact	Censored
B3	Death after the start of any subsequent antineoplastic therapy	Date of death	Event
C	Patient alive and without progression on their subsequent antineoplastic therapy	Date of last contact	Censored

	Situation	Event Date	Outcome
D	Patient alive, without starting a subsequent antineoplastic therapy	Date of last contact	Censored

Procedures related to COVID-19 pandemic (e.g. quarantine, patient isolation, testing, etc) will be listed on an individual basis, with reported term, MedDRA Preferred Term (PT) and Lowest Level Term (LLT), and dates, day relative to first study treatment administration and status with respect to the study treatment period. Procedures related to COVID-19 are reported in the eCRF with a prefix “COVID19” and will be coded using appropriate MedDRA codes. Prefix will not be displayed in the listing.

